Dose adjustments for safety (Section 6.2.2), and reinstatement of doses (Section 6.2.3) will apply whether the patient is on the original dose, or a dose that was increased for lack of efficacy.

6.2.1.2 Dose modification for patients starting INC424 at a dose of 5 mg BID

6.2.1.2.1 Dose increases at week 4

For those patients who start INC424 treatment at a dose of 5 mg BID, dose increases can be made as described below. The dose can be escalated 5 mg once a day starting at week 4, and thereafter no more than every two weeks ONLY if:

- Inadequate efficacy is seen with the current dose level (See [Section 6.2.1.1.1](#))
- No treatment-related toxicity has occurred with the current dose level, resulting in treatment reduction or interruption or discontinuation in the previous 28 days
- The minimum platelet count at the time of the escalation is $\geq 50,000/\mu\text{L}$
- ANC $> 1000/\mu\text{L}$ since last scheduled visit
- The total dose may never exceed 25 mg BID

[figure not shown]
If the above criteria are met, then the INC424 dose can be increased by 5 mg o.d. e.g., from 5 mg BID to 5 mg QAM and 10 mg QPM.

6.2.1.2.2 Dose increases beyond week 4

After Week 4, dose increases of INC424 are allowed for those patients who exhibit an INCREASE in palpable spleen length. The rules for these optional dose increases are as follows:

- The dose increases may only occur if the platelet count and ANC data for that visit are available.
- The palpable spleen length for that Study Visit must show a 2 cm or greater INCREASE in length compared to the on-study nadir (lowest palpable spleen measurement during the study, including Baseline).
- The patient must NOT have had a prior safety-related dose reduction.
- The following platelet threshold have been met:
 - The patient must have had a platelet count $\geq 50,000/\mu\text{L}$ at every assessment since Baseline for those starting INC424 at a starting dose of 5 mg BID
- The patient must have had ANC $\geq 1000/\mu\text{L}$ at every assessment since baseline.
- The dose increase may only be an increase of 5 mg once daily for those starting on an INC424 dose of 5 mg BID.
- The total dose may never exceed 25 mg BID.
- Following a dose increase, platelet count and ANC levels should be assessed approximately 2 weeks after the dose adjustment. If a regularly scheduled Study Visit does not coincide with this required blood draw, an unscheduled Interim Visit should be held to collect samples for hematology.

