6.2.3 Restarting or reinstating previous dose

6.2.3.1 Restarting or reinstating previous dose for patients who start INC424 15 – 20 mg BID

Dosing of INC424 may be restarted or increased following recovery of platelet counts and/or ANC to acceptable levels as illustrated in [Table 6-4](#) for those patients who start on INC424 15 – 20 mg BID. The objective for restarting or escalating after a reduction for safety is to find the highest safe dose of INC424 for each patient, with increases in dose generally not more than in increments of 5 mg BID and not more often than every 2 weeks. Patients who are restarting after a reduction for thrombocytopenia may not receive doses above 20 mg BID maximum. Similarly, ANC levels that decline to < 500/ μ L necessitate immediate dose interruption ([Section 6.2.6](#)). ANC level recovery to 500 / μ L and above but less than 750/ μ L will allow dosing to be restarted at 5 mg BID, and ANC levels between 750/ μ L, but < 1000/ μ L may restart at 10 mg BID. Absolute neutrophil count level increases to above 1000/ μ L will allow a further dose increase to a maximum of 20mg BID.

The maximum dose used should never exceed 5mg BID LESS than any dose that resulted in platelets falling below 100,000/ μ L or ANC falling below 500/ μ L. After restarting using the guidelines in [Table 6-4](#), if it is found that a patient cannot tolerate the lowest allowed dose (5mg BID, or 5mg QD with concomitant CYP3A4 inhibitor, see [Section 6.2.4](#)) without platelets falling below 50,000/ μ L, neutrophils falling below 500/ μ L, or Hgb falling below 6.5g/dL despite the use of transfusion therapy, drug must be permanently discontinued ([Section 6.2.6](#), and [Section 7.6.1](#)).

Table 6-4 **Restarting or increasing INC424 dose after safety interruptions or dose reductions for patients starting on doses of 15 – 20 mg BID**

Current Platelet Count	Dose Restart or Dose Increase Guidelines
< 50,000/ μ L	Continue hold
50,000/ μ L to < 75,000/ μ L	5 mg BID for at least 2 weeks; if stable, may increase to 10 mg BID
75,000/ μ L to < 100,000/ μ L	10 mg BID for at least 2 weeks; if stable, may increase to 15 mg BID
100,000/ μ L to < 125,000/ μ L	15 mg BID
\geq 125,000/ μ L	20 mg BID
Current ANC Level	Dose Restart or Dose Increase Guidelines
< 500/ μ L	Continue hold
500 to < 750/ μ L	5 mg BID for at least 2 weeks; if stable, may increase to 10 mg BID
750 to < 1000/ μ L	10 mg BID for at least 2 weeks; if stable, may increase to 15 mg BID

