1000 to < 1500/ μ L	15 mg BID for at least 2 weeks; if stable may increase to 20 mg BID
\geq 1500/ μ L	20 mg BID

NOTE: Whether the dose interruption occurred because of neutropenia, thrombocytopenia or both, when restarting, both the platelet count and ANC must be considered to determine the restart dose, with the lower calculated dose being used.

6.2.3.2 Restarting or reinstituting previous dose for patients who start INC424 at 5 mg BID

Dosing of INC424 may be restarted or increased following recovery of the platelet count to $\geq 50,000/\mu\text{L}$. Reinitiate treatment at a dose of 5 mg o.d. The dose may be increased by 5 mg o.d. every two weeks based on platelet counts and the absence of other adverse events.

When the ANC is $< 500/\mu\text{L}$, hold INC424 dosing. INC424 can be reinitiated in this population once the ANC is $\geq 500/\mu\text{L}$, at a dose of 5 mg o.d. The dose may be increased by 5 mg o.d. every two weeks based on platelet counts and the absence of other adverse events.

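### In Protocol 6.2.3.2, re-escalation after a neutropenia hold in 5 mg BID starters is tied to platelet counts and names no ANC condition, which conflicts with the ANC rules for increases elsewhere in the protocol

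*Protocol*

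**What the plan says.** Protocol 6.2.3.2 covers restarting in 5 mg BID starters and has two paragraphs.

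- **Platelet paragraph.** After platelets recover to 50,000/µL or more: "Reinitiate treatment at a dose of 5 mg o.d. The dose may be increased by 5 mg o.d. every two weeks", subject to platelet counts and the absence of other adverse events.
- **ANC paragraph.** Drug is held when ANC is below 500/µL. "INC424 can be reinitiated in this population once the ANC is" at least 500/µL, again at 5 mg o.d. The paragraph then ends: "The dose may be increased by 5 mg o.d. every two weeks based on platelet counts and the absence of other adverse events".

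The closing sentence is the same in both paragraphs. In the second, ANC governs the hold and the restart but is not mentioned for the increases.

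Other places set ANC conditions for dose increases in 5 mg starters. The synopsis (dose, regimen, treatment) and 6.2.1.2.1 both require ANC above 1000/µL since the last scheduled visit. Section 6.2.1.2.2 requires ANC of at least 1000/µL at all assessments from baseline on. Section 6.2.3.2 refers to none of them.

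**The concern.** A paragraph about neutropenia carries a re-escalation rule keyed to a different count. The sentence may have been carried over from the platelet paragraph, though that is inference.

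What is at stake is individual dosing safety. If the patient was on the 5 mg BID starting dose when ANC fell below 500/µL, the first permitted step returns that patient to the dose on which the fall occurred, with no ANC condition stated for taking it. A site that follows 6.2.3.2 literally may take the step; a site that applies the synopsis list may wait for ANC above 1000/µL, or may conclude that no increase is allowed at all.

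**Working it through.** The protocol gives no figure to reproduce here. The check is a comparison of texts plus simple dose arithmetic.

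**Doses under 6.2.3.2**
- Restart: 5 mg o.d. = 5 mg/day.
- First step: 5 + 5 = 10 mg/day, which is 5 mg BID, at the earliest 14 days after restart.
- Second step: 10 + 5 = 15 mg/day, at the earliest 2 × 14 = 28 days after restart.
- ANC at which these steps are open on the paragraph's own words: 500/µL and above. Against the limit of 1000/µL in the synopsis and 6.2.1.2.1, the uncovered range is 500 to 1000/µL.

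**Could another text supply the ANC condition?**

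| Text | ANC condition | Does it govern re-escalation after an ANC hold? |
|---|---|---|
| Synopsis list, 5 mg starters | Above 1000/µL since last scheduled visit | Same population, step size and minimum interval, and no efficacy condition. But it excludes anyone with an earlier safety-related dose reduction |
| 6.2.1.2.1 | Above 1000/µL since last scheduled visit | Only where "Inadequate efficacy is seen with the current dose level"; also excludes toxicity-driven reduction or interruption in the previous 28 days |
| 6.2.1.2.2 | At least 1000/µL at all assessments from baseline on | No. It concerns spleen growth: "After Week 4, dose increases of INC424 are allowed for those patients who exhibit an INCREASE in palpable spleen length". A held patient has had ANC below 500/µL, and 500 < 1000, so the condition always fails |
| NOTE under Table 6-4 | Both counts | Restart dose only, in the section for 15–20 mg starters: "when restarting, both the platelet count and ANC must be considered to determine the restart dose, with the lower calculated dose being used" |
| 6.2.6, sponsor approval | None | Covers the restart, not later increases |

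**The synopsis bar.** The protocol does not say whether a hold followed by a restart at a lower dose is a safety-related reduction. SAP 3.2 classes a stop followed by a lower dose as both an interruption and a reduction. That is a convention for classifying dose records, not a dosing rule, so it supports one reading without settling it. The two readings are:
- If it is a reduction (10 mg/day, then 0, then 5 mg/day), the synopsis forbids every later increase that 6.2.3.2 permits.
- If it is not, the synopsis permits the increase only at ANC above 1000/µL and with no recent safety interruption, while 6.2.3.2 permits it from 500/µL.

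On either reading the two texts disagree.

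**The case against.** The strongest case on the other side has four parts.

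1. **An ANC rule for increases in this population already exists.** This is right. The synopsis list has no efficacy or spleen condition and requires ANC above 1000/µL. A reader might infer from 6.2.3.2 that the protocol sets no ANC limit anywhere that could apply to these increases; the documents do not support that. What stands is narrower: the synopsis list does not cleanly fill the gap, because its bar on earlier safety-related reductions may exclude these very patients.

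2. **The dose reached is not extreme by the protocol's own standard.** This also stands. In 15–20 mg starters with ANC of 500 to below 750/µL, Table 6-4 gives "5 mg BID for at least 2 weeks; if stable, may increase to 10 mg BID", so 10 mg/day is accepted at restart. Those patients differ in baseline platelet count, and 6.2.3.1 adds two protections that 6.2.3.2 lacks: further steps within that tier depend on stability, and the dose is capped at 5 mg BID below any dose on which ANC fell below 500/µL.

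3. **Neutropenia requiring a hold is itself an adverse event** under 9.1.1 and 9.1.2.1, and is followed until normal or explained, so an open event would block the step. This is a reasonable reading. But the word *other* leaves unclear whether the event that caused the hold counts, and a dosing rule should not turn on that.

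4. **Safeguards remain.** The hold below 500/µL applies to all patients (6.2.2). Weekly counts are advised when neutrophils are below 1000/µL (7.5). The synopsis calls for platelets and ANC about two weeks after an increase. Increases are optional and rest on investigator judgement. These limit the harm but do not set an ANC condition for taking the step.

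**Conclusion.** The point holds as a minor dosing-safety correction. The ANC paragraph of 6.2.3.2 ties re-escalation to platelet counts rather than to the count that caused the hold, and it conflicts with the synopsis. Read alone, it permits a step from 5 to 10 mg/day from day 14 after restart, and further steps at two-week intervals, with no ANC condition in the range 500 to 1000/µL.

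This rests on two assumptions: that 6.2.3.2 is read on its own terms, since it refers to no other ANC rule, and that the patient was on 5 mg BID when held, for the claim that the first step restores the earlier dose. The documents do not say how many 5 mg starters were held for ANC, so no patient count is claimed.

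Two stronger readings should be avoided. The text does not show that neutropenic patients are escalated without protection, given the continuing hold and monitoring. Nor does it bear on the statistical analysis: no SAP estimate depends on this rule.

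**What to change.** In the ANC paragraph of 6.2.3.2:
- Name ANC alongside platelet counts in the closing sentence, keeping the adverse-event condition.
- Require ANC above 1000/µL since the last scheduled visit for each increase, matching the synopsis and 6.2.1.2.1.
- State that the synopsis bar on earlier safety-related reductions does not apply to re-escalation under 6.2.3.2.

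A stability condition modelled on Table 6-4 would be weaker: an ANC unchanged at 550/µL for two weeks could pass it.

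The cost is a few words in a clarification letter or the next amendment, for patients still on treatment. Enrolment closed on 31 December 2014, and the current protocol expects the last visit in December 2016. No new assessment is needed, because ANC is part of routine hematology. The downside is slower re-escalation: patients whose ANC stays between 500 and 1000/µL would remain at 5 mg o.d.

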6.2.4 Dose reductions for concomitant CYP inhibitor usage

INC424 is metabolized in the liver by the cytochrome (CYP) P450 metabolizing enzyme system, predominantly by the 3A4 isoenzymes. With concomitant dosing of strong (potent) CYP inhibitors such as oral ketoconazole, plasma exposure of INC424 increases approximately 2-fold. Thus, a dose reduction of $\sim 50\%$ for INC424 is appropriate for patients who take ketoconazole or other potent CYP3A4 inhibitors as concomitant medication. Twice daily (BID) doses will be decreased to the corresponding once daily dose as follows:

- If dose is 25 mg BID, change dose to 25 mg **QD**
- If dose is 20 mg BID, change dose to 20 mg **QD**
- If dose is 15 mg BID, change dose to 15 mg **QD**
- If dose is 10 mg BID, change dose to 10 mg **QD**
- If dose is 5 mg BID, change dose to 5 mg **QD**

If a patient is already on a once daily dose of INC424, and a potent CYP3A4 inhibitor is added as a concomitant medication, the dose should be reduced to 5 mg every other day.

More frequent monitoring of hematology parameters and clinical signs and symptoms of ruxolitinib related adverse reactions is recommended upon initiation of a strong (potent) CYP3A4 inhibitor.

Potent inhibitors of CYP3A4 include oral ketoconazole, clarithromycin, itraconazole, voriconazole, nefazodone, telithromycin ([Flockhart 2007](#)). Based on the very low overall bioavailability of topical ketoconazole, no dosage adjustment is needed for use with topical ketoconazole. NOTE: once the course of therapy using a CYP 3A4 inhibitor has been completed, the patient should resume their prior BID dose regimen of INC424 beginning the next day.

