1.3.1 INC424 pharmacokinetics

Fifteen Phase I, nine Phase II and three Phase III clinical studies (two in MF, one in PV) provided clinical pharmacology data on ruxolitinib in healthy volunteers and in patients with MF, ET, PV, subjects with renal or hepatic impairment, prostate cancer, pancreatic cancer, multiple myeloma (MM) or rheumatoid arthritis (RA).

Oral absorption of ruxolitinib is rapid and nearly complete, with $\geq 95\%$ absorption indicating high *in vivo* permeability in the human gastrointestinal tract, consistent with a Biopharmaceutical Classification System (BCS) Class I compound. Mean peak plasma concentration (C_{max}) is achieved 1-2 h post-dose. The effect of food on ruxolitinib exposure is minimal and is not expected to be clinically significant; as a result, the drug may be administered either with or without food.

Dose proportional exposure is observed between 5 and 200 mg dose range with linear pharmacokinetics (PK). Plasma protein binding is approximately 97% *in vitro*. There is moderate distribution to organs and tissues with no long-term retention of drug-related material in preclinical species and limited drug penetration into the central nervous system (CNS) or across the blood-brain barrier. There was $>95\%$ [¹⁴C] drug recovery in a mass balance study with 74% and 22% of the dose excreted in urine and feces of healthy subjects, respectively. Less than 1% of the administered dose is recovered in urine and feces as unchanged parent drug. The mean terminal elimination half-life (T_{1/2}) is ~ 3 h with no appreciable accumulation of either parent or metabolites with twice daily dosing.

Metabolism is predominantly via the cytochrome P450 isozyme CYP3A4 to yield oxygenated and subsequent conjugated metabolites. Oxidative metabolites of ruxolitinib retain pharmacological activity albeit with one half to one fifth of the activity of the parent compound. *Ex vivo* pharmacokinetic/pharmacodynamic (PK/PD) analysis indicates that the total of 8 active metabolites contribute to 18% of the overall PD activity of ruxolitinib.

When administering ruxolitinib with strong CYP3A4 inhibitors, the total daily dose should be reduced by approximately 50%.

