5.1 Patient population

Adult male or female patients ≥ 18 years of age diagnosed with PMF, PPV MF, or PET-MF who have either received prior treatment with commercially available agents, investigational drug or never received treatment are eligible for this Expanded Access Study.

All relevant medical and other considerations should be taken into account when deciding whether this protocol is appropriate for a particular patient. To maximize patient safety, patients should be treated on this protocol only at centers having ready and adequate staff to care for the thrombocytopenic patient. Physicians should consider the risks and benefits of any therapy and, therefore, only enroll patients for whom the agents administered are appropriate. Although they will not be considered as formal eligibility criteria, as part of this decision-making process physicians should recognize that the following may increase the risk to the patient entering this protocol: physicians should be aware that studies show CYP3A4 is the major human CYP450 isoenzyme catalyzing biotransformation of INC424. A clinical study where a strong CYP3A4 inhibitor (ketoconazole) and INC424 was co-administered resulted in a 90% increase in AUC of INC424. Thus, INC424 dose should be adjusted when co-administration with a strong CYP3A4 inhibitor (see [Section 6.2.4](#)). Other CYP3A4 inhibitors or inducers are to be dosed with caution.

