6.1 Investigational treatment, other study treatment, supportive treatment

6.1.1 Study drug dosing

All eligible patients with PMF, PPV MF, or PET MF who consent to participate in this study will receive INC424 open-label investigational drug provided free of charge by Novartis Pharmaceuticals at a dose of 5 – 25 mg BID [dose based on Baseline platelet count] until either:

[figure not shown]
- Disease progression;
- Transplant;
- Unacceptable toxicity;
- Death;
- Discontinuation from the study for any other reason;
- Physician decision
- Withdrawal of informed consent;
- Until 24-months after LPFV; or
- Until the drug is commercially available, whichever occurs first.

The starting dose of INC424 will be determined based on baseline platelet counts as follows:

- Patients with a baseline platelet count of > 200,000/ μ L will begin dosing at 20 mg PO BID.
- Patients with a baseline platelet count of between 100,000/ μ L – 200,000/ μ L (inclusive) will begin dosing at 15 mg PO BID.
- Patients with a Baseline platelet count of 50,000/ μ L – <100,000/ μ L / μ L will begin dosing at 5 mg BID (one 5 mg tablet BID)
- Patients with platelet counts less than 50,000/ μ L are ineligible for the study (see [Section 5.2](#) and [Section 5.3](#)).

Dosage Tablet Combinations for Patients

For 25 mg PO BID	For 20 mg PO BID	For 15 mg PO BID	For 10 mg PO BID	For 5 mg PO BID
Two 10 mg tablets	Four 5 mg tablets	One 10 mg tablet and	One 10 mg tablet	One 5 mg tablet

For 25 mg PO BID	For 20 mg PO BID	For 15 mg PO BID	For 10 mg PO BID	For 5 mg PO BID
and one 5mg tablet		one 5 mg tablet		
One 10 mg tablet and three 5 mg tablets	Two 10 mg tablets	Three 5mg tablets	Two 5 mg tablets	
Five 5 mg tablets	Two 5 mg tablets and one 10 mg tablet			

INC424 tablets will be administered orally without regards to food in an outpatient setting in accordance with the specified dosing schedules. The dosage strength is 5 mg or 10 mg per tablet INC424. INC424 tablets are to be taken orally BID, approximately 12 hours apart (morning and night). INC424 will be self-administered by the patient, and each investigator should instruct the patient to take the study drug as per protocol (if applicable). All dosages prescribed and dispensed to the patient and all dose changes during the study must be recorded on the Dosage Administration Record (DAR) eCRF.

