6.3.2 Permitted concomitant therapy requiring caution and/or action

The following medications have *restrictions on use* or doses or require changes to the way in which INC424 is administered during the study:

- In patients for whom warfarin or heparin use will be initiated, the degree of thrombocytopenia should be considered, coagulation parameters monitored, and dose of anticoagulant adjusted accordingly. If anticoagulation is required during INC424 administration, low molecular weight heparin is preferred, particularly in patients who are: elderly, history of CHF, diabetic, hepatic or renal disease, or atrial fibrillation (first episode).
- Low dose aspirin (\leq 150 mg/day) and non-steroidal anti-inflammatory agents (acetaminophen, ibuprofen) may be used. Aspirin doses $>$ 150 mg are prohibited.
- Inducers or inhibitors of the metabolizing enzyme CYP3A4 ([Appendix VI](#)):
- When concomitant administration of a strong (potent) inhibitor of CYP3A4 metabolizing enzymes or dual CYP2C9/CYP3A4 inhibitors ([Appendix VI](#)) is required for patient management, the dose of INC424 tablets must be reduced by approximately 50% to be administered twice daily by decreasing the twice daily dose or by decreasing the frequency of dosing to the corresponding once daily dose when twice daily dose is not practical.” (See [Section 6.2.4](#)).

• Note: No dose adjustment of ruxolitinib is needed for use with topical ketoconazole. Note: More frequent monitoring of hematology parameters and clinical signs and symptoms of ruxolitinib related adverse reactions is recommended upon initiation of a strong (potent) CYP3A4 inhibitor

- No dose adjustment will be made when moderate systemic CYP3A4 inducers ([Appendix VI](#)) are co-administered with study treatment.
- Granulocyte growth factors are not allowed while study treatment is being administered but may be used for severe neutropenia at the Investigator's discretion while study medication is being withheld.
- Certain herbal supplements see [Appendix VI](#) are prohibited. Because the composition, pharmacokinetics and metabolism of many herbal supplements are unknown, the concurrent use of all herbal supplements is strongly discouraged during the study however if used during the trial please ensure the treatment is entered on the proper eCRF page (see [Section 6.3.1](#)).

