6.5.2 Study drug packaging and labeling

INC424 investigational drug is provided as 5 mg and 10mg tablets. INC424 5 mg and 10mg tablets are packaged in bottles or in blisters according to local Heath Authority requirements. Medication labels will be in the local language and comply with the legal requirements of each country. They will include the patient number, but no information about the patient.

Patients will initially receive a 4-week supply of INC424 each month for the first 3 months of the study. Once the study visits expand to every 3 months, patients will have a 3-month supply of INC424 dispensed. Immediately before dispensing the study drug to the patient, the investigator or his/her designee will detach the outer part of the label from the packaging and affix it to the source document containing the patients' unique patient number (identifier).

INC424 treatment will be administered until either:

- Disease progression;
- Transplant;
- Unacceptable toxicity;
- Death;
- Discontinuation from the study for any other reason;
- Physician decision
- Withdrawal of consent;
- Until 24-months after LPFV; or
- Until the drug is commercially available, whichever occurs first

Should INC424 not be available to patients after the drug is commercialized or 24-months after LPFV, Novartis will have a local transition plan in place to ensure that patients have access to INC424 without delays to treatment.

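### With a potent CYP3A4 inhibitor, Sections 6.2.4 and 6.3.2 give different schedules at 20 mg BID (and at 10 mg BID when 5 mg tablets are to hand), and the 6.2.4 return note sends once-daily patients to a BID dose they were not taking

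*Protocol*

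**What the plan says.** **BID patients.** Protocol Section 6.2.4 aims for a cut of about 50% with a potent CYP3A4 inhibitor. It states "Twice daily (BID) doses will be decreased to the corresponding once daily dose as follows" and lists 25, 20, 15, 10 and 5 mg BID, each becoming the same number of milligrams once daily. Section 6.3.2 instead wants the dose "reduced by approximately 50% to be administered twice daily by decreasing the twice daily dose". It permits once-daily dosing only as a fallback, worded "or by decreasing the frequency of dosing to the corresponding once daily dose when twice daily dose is not practical", and then points to 6.2.4. Section 6.5.2 states "INC424 investigational drug is provided as 5 mg and 10mg tablets". The table in 6.1.1 headed "Dosage Tablet Combinations for Patients" has columns for both 10 mg BID and 5 mg BID.

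**Once-daily patients.** For a patient already on once-daily dosing when the inhibitor is added, 6.2.4 says "the dose should be reduced to 5 mg every other day". These are chiefly patients who started on 5 mg BID (baseline platelets 50,000 to below 100,000/µL). They reach 5 mg once daily by a platelet reduction (6.2.2.2, Table 6-3) or by restarting after a hold (6.2.3.2).

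**After the inhibitor.** The closing note of 6.2.4 has the patient go back, the next day, to the twice-daily regimen used before. It makes no provision for a patient who was on once-daily dosing.

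**Stop rules.** Sections 6.2.6 and 7.6.1 define the lowest allowed dose as 5 mg BID, or 5 mg once daily with an inhibitor. Section 7.6.1 adds low-platelet patients to the once-daily case. Neither names 5 mg every other day.

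**The concern.** These are rules that sites act on. Enrolment has closed, but treatment was planned to run to December 2016, so they govern patients on drug. Inhibitor use was foreseen: clarithromycin and voriconazole are named as potent inhibitors in 6.2.4 and also appear in the Appendix IX list.

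A site treating a patient at 20 mg BID finds one section telling it to give 20 mg once and another telling it to give 10 mg twice. The return note matters more, because it bears on the group most prone to thrombocytopenia. A patient cut from 5 mg BID to 5 mg once daily because platelets fell below 50,000/µL could, on a literal reading, be put back the next day on the dose at which they fell.

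**Working it through.** **1. The plan's own figure.** Dropping from d mg BID to d mg once daily takes 2d mg/day to d mg/day, a cut of 1 − d/2d = 50%. This reproduces the stated reduction. Section 5.1 reports that a strong inhibitor "resulted in a 90% increase in AUC of INC424" (1.9-fold), and 6.2.4 says about 2-fold. Half the dose therefore gives 0.5 × 1.9 = 95% to 0.5 × 2.0 = 100% of the exposure before the inhibitor.

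**2. The two conversions side by side**, using 5 and 10 mg tablets:

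| Dose before | 6.2.4 | 6.3.2, kept twice daily | Daily total, both | Schedules conflict? |
|---|---|---|---|---|
| 25 mg BID | 25 mg once | 15 + 10 mg (unequal) | 25 mg | Only if an unequal split counts as practical |
| 20 mg BID | 20 mg once | 10 + 10 mg | 20 mg | Yes |
| 15 mg BID | 15 mg once | 10 + 5 mg (unequal) | 15 mg | Only if an unequal split counts as practical |
| 10 mg BID | 10 mg once | 5 + 5 mg | 10 mg | Yes, if 5 mg tablets are to hand |
| 5 mg BID | 5 mg once | not possible (2.5 mg) | 5 mg | No |

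- Daily totals agree in 5 of 5 rows.
- At 20 mg BID, each tablet combination listed in 6.1.1 (four 5 mg; two 10 mg; two 5 mg and one 10 mg) allows a 10 mg dose. The 6.3.2 fallback to once daily is therefore not triggered on tablet grounds.
- At 10 mg BID, 6.1.1 allows a single 10 mg tablet per dose. A patient holding only those cannot take 5 mg BID until new tablets are dispensed.
- Where the schedules differ, the single dose under 6.2.4 is 20/10 = 10/5 = 2.0 times as large.
- The unequal-split wording in 6.2.2.3 and 6.2.2.4 is written for renal and hepatic impairment, not for inhibitors.
- 5 mg in the morning and 10 mg in the evening (6.2.1.2.1) has no row in 6.2.4. Half of 15 mg/day is 7.5 mg/day, which 5 mg tablets cannot give on a daily basis.

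**3. The every-other-day dose.** 5/2 = 2.5 mg/day on average, 50% of 5 mg once daily. With the inhibitor it is equivalent to 2.5 × 1.9 = 4.75 to 2.5 × 2.0 = 5.0 mg/day, or 95% to 100% of 5 mg once daily without one. The dose itself is sound.

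**4. The return note for a patient on 5 mg once daily.**

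- Literal return to 5 mg BID: 10 mg/day.
- Against the dose before the inhibitor: 10/5 = 2.0 times.
- Against the equivalent on the inhibitor: 10/5.0 = 2.0 to 10/4.75 = 2.1 times.
- Under 6.2.3.2, which allows increases of 5 mg once daily every two weeks depending on platelet counts, the same rise takes (10 − 5)/5 = 1 step, or two weeks. The literal note makes it the next day.

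**5. Effect on the analysis.** SAP Section 3.2 defines dose intensity as cumulative dose divided by days of exposure. Equal daily totals give equal dose intensity under either BID conversion.

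**The case against.** **On the schedule.** Section 6.3.2 offers two routes to the same 50% cut and refers to 6.2.4, so 6.2.4 can be read as simply applying the second route. Practicality is not defined. Section 6.5.4.1 allows up to an 84-day supply, and between-visit dose changes are made by telephone, so once daily may be the only workable route for a patient holding 10 mg tablets. This stands in part and is why the conflict at 10 mg BID is conditional. It does not remove the conflict at 20 mg BID, because 6.2.4 carries neither the twice-daily preference nor the practicality test. Section 1.3.1 speaks only of total daily dose and does not decide between the two.

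**On the return note.** It plainly has in mind the BID patients in the list above it, and an investigator would probably resume 5 mg once daily. That limits the practical effect. But the section also covers once-daily patients, and its text gives them no other instruction.

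**On the stop rules.** A reader might infer that a low-platelet patient on an inhibitor falls outside both rules. The wording does not support that: the inclusive link in 7.6.1 takes in a patient who meets both conditions, and 6.2.6 applies to anyone on an inhibitor. What remains is only that the every-other-day dose is not named.

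**On safety.** Platelet and ANC holds still apply, 7.5 advises weekly counts below 100,000/µL, more frequent haematology is recommended when an inhibitor starts, and Appendix VI discourages CYP3A4 inhibitors altogether. All of this stands.

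**Conclusion.** Two operative rules need correcting; the point is minor. The schedules conflict at 20 mg BID, and at 10 mg BID on the assumption that 5 mg tablets are to hand. The return note, on the assumption that a site follows it literally, gives at least 2 times the pre-inhibitor dose in once-daily patients and skips the two-week step. The unnamed every-other-day dose is a lesser wording point.

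Three stronger readings are not supported:

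- **Different amounts of drug.** The two sections do not give this; daily totals match in every row. The documents attach no clinical meaning to the 2.0-fold difference in single dose.
- **A larger jump on return.** A reader could construct one: a 5 mg starter raised to 10 mg BID, held, restarted at 5 mg once daily, then given an inhibitor, would literally return to 20 mg/day, 20/5 = 4.0 times. Nothing in the documents suggests that this sequence occurs.
- **Distorted safety results.** Dose intensity is the same under both conversions, and the effect on the descriptive adverse event tables should be negligible.

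The documents do not give the number of patients affected.

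**What to change.** 1. Reword the return note in 6.2.4: *resume the dose taken before the inhibitor, unless 6.2.2 requires a lower dose.*
2. Make 6.2.4 and 6.3.2 give one schedule. One option is 20 mg BID to 10 mg BID, 10 mg BID to 5 mg BID, and 5 mg BID to 5 mg once daily, with a stated rule for 25 mg BID, 15 mg BID and the 5 mg morning/10 mg evening regimen. The documents do not show which schedule is preferable; what matters is that there is only one.
3. Keep the every-other-day instruction for all patients already on once-daily dosing. Restricting it to 5 mg once daily would leave others without a rule, such as a patient on 10 mg once daily because of one inhibitor who is given a second. Name that dose in 6.2.6 and 7.6.1. Section 6.2.3.1 covers 15–20 mg starters and needs no edit.

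The cost is amendment wording or a clarification letter to sites. No new data, visits or patients are needed, and the SAP does not change.
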